**Table 3. Eligibility Criteria**

[figure not shown]

• <math>\geq 3</math> systolic blood pressure measurements <math>\geq 140/90</math> mmHg (in the previous 12 months including one in the 3 months prior to invitation to participate)

• Age 18-85 years

• Weight <math><300</math> pounds

• Has a cell phone

• Consent

---

**Aim 3. Obtain demographic and other data on potentially eligible participants using an on-line questionnaire.** We will collect demographic data at time of enrollment including date of birth, sex, race/ethnicity, zip code of residence, country of birth, years of residence in the U.S., years of education completed, family income in wide categories to avoid non-response, current health insurance (Medicare [including managed care plans], Medicaid, VA/Tricare, commercial,

none), and whether the individual has a regular health care provider. In addition, we will collect data on other potential confounding variables including smoking, alcohol and caffeinated beverage consumption, smoking, exercise, height, weight, and baseline BP medications. We will also collect data on health care utilization, specifically physician/RNP office and emergency department/urgi-care visits. We will base the data collection instrument on forms used in the MESA study, where these variables have been collected among participants of varying levels of health literacy. These forms are available in Spanish and English.

**Aim 4. Pilot test the text messaging intervention and document BP control rate in response to the intervention in a pilot study of N=70 per group.** Once the intervention messages have been developed, pre-tested, and approved by our IRB, we will conduct a pilot of the study procedures using 5-10 volunteers, specifically of the enrollment, intervention, and data collection procedures. Once we are satisfied that the procedures are working as expected, we will conduct a pilot study randomizing 70 individuals to each group. We chose this sample size for the pilot as 10% of the planned full scale trial and therefore sufficient to demonstrate that all study procedures including recruitment are feasible and realistic and to provide a preliminary signal of the intervention effect. The intervention group will receive text messages as described below. The comparison group will receive usual care. Blood pressure measures will be obtained in both groups at baseline and at 3, 6, and 12 months. A reduced questionnaire will be administered at 12 months to ascertain insurance and health care provider status at that time. Compensation (up to \$200 by Bank of America pay card) will be sent by mail to all individuals who complete the blood pressure checks at 3, 6 and 12 months follow up.

**Intervention.** Individuals randomized to intervention will receive usual care (see below) plus intervention. The intervention will consist of additional communication via interactive text messaging. If the blood pressure is  $\geq 140/90$  mm Hg at a measurement occasion including baseline, individuals will receive a text message advising them to see a health care provider to receive care for high blood pressure, that the minimal goal is  $<140/90$  mmHg for people with hypertension, and asking them to return to a higi kiosk in 2 weeks to have the blood pressure taken. A reminder to return will be sent both one week and two days prior to the 2-week due date. For the reminder 2 days before, individuals will be asked to respond whether they saw or spoke to a health care provider for their elevated blood pressure. Regardless of response they will be asked to return to a higi kiosk to have their blood pressure checked. If the individual does not return to the higi kiosk, he or she will be sent a text message weekly gently urging them to come in to have their blood pressure assessed. These messages will also include other educational information as outlined in section C.5 (table 2). In addition, these messages will include advice to see a health care provider for further assessment and treatment of high blood

pressure. If the kiosk blood pressure level remains elevated, these individuals will continue in the text message loop, with additional educational and interactive message options. The figure above is an example of such a loop. If their blood pressure is  $<140/90$  mm Hg, they will be congratulated on improving their blood pressure, reminded to maintain contact with their health care provider for blood pressure management, and asked to return in 1 month for a recheck. Reminders for this blood pressure check will be sent one week and 2 days before and will continue to be sent weekly if they do not return.

**Usual Care.** Individuals randomized to usual care will receive the health information currently provided to individuals measuring their BP at a higi health kiosk, who are informed on the screen that their BP level falls into one of five categories, with advice for those in the highest category ( $\geq 180$  systolic or  $110$  mmHg diastolic) to seek emergency medical care. The screen seen by individuals with systolic  $\geq 140$  mmHg is shown in the graphic.

**Aim 5. Pilot test secure data transfer and other DCC functions.** All study-specific data will be managed by the DCC. Blood pressure measurements obtained at kiosks will be securely transferred to the DCC via an automated web service employing a secure sockets layer (SSL) over encrypted https. The DCC will host a secure website on which consent and questionnaire data will be obtained and also the messaging server for the intervention. Enrollment, follow up blood pressure measurements, and intervention messaging will be monitored weekly by the investigators through reports created by the DCC. The DCC will perform statistical analysis of the study data.

The main approach will be data summarization as we do not expect statistical significance in the pilot study. The DCC will also provide reports to the DSMB.

Title: Retail Outlet Health Kiosk Hypertension Trial (ROKHyT)

Registration#: NCT03515681

Protocol Version Date: 15APR2019

Statistical Analysis Plan

The overall goal of the R34 pilot grant is to develop pilot data for an application for a fully powered trial. The intervention using interactive text messaging will be compared to current information provided in the context of higi installation (usual care). The primary endpoint will be hypertension control defined as < 149/90 mmHg at 12 months post randomization. Measurements will also be obtained at 3- and 6-months post randomization.

The specific aims are shown in table 1.

Table 1. Specific Aims
1. Develop and pre-test the intervention text messages
2. Pilot the enrollment, consent, randomization, and data collection procedures at baseline and 3, 6, and 12 months and document participation and completion rates in a randomized pilot study of N=70 per group.
3. Obtain demographic data on potentially eligible participants using an on-line questionnaire.
4. Pilot test the text messaging intervention and document blood pressure control rate in response to the intervention.
5. Pilot test secure data transfer and other data coordinating center (DCC) functions.

Aim 1. No statistical analysis.

Aim 2. The numbers enrolled, consented, and randomized will be tabulated.

Aim 3. Demographic characteristics will be tabulated.

Aim 4. The proportion in each group (intervention and control) achieving blood pressure control at 12 months will be tabulated and the difference between these proportions will be calculated. Control will be defined as systolic blood pressure <140 mmHg and diastolic blood pressure <90 mmHg. A Mantel-Hanzel relative risk with adjustment for stratification will be calculated comparing the two groups. In addition, the proportions achieving blood pressure control at 3-months and 6-months follow-up will also be tabulated. Formal statistical testing will not be done because the pilot study is not powered for hypothesis testing.

Aim 5. No statistical analysis.

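### The SAP gives two systolic cut-offs for 12-month blood pressure control, 149 mmHg in the primary-endpoint sentence and 140 mmHg in Aim 4

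*SAP*

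**What the plan says.** The SAP names its primary endpoint once, in the opening paragraph: "The primary endpoint will be hypertension control defined as < 149/90 mmHg at 12 months post randomization".

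Under Aim 4 it defines control again: "Control will be defined as systolic blood pressure <140 mmHg and diastolic blood pressure <90 mmHg". That paragraph also lists what will be computed. The proportion in each group "achieving blood pressure control at 12 months will be tabulated and the difference between these proportions will be calculated". Then: "A Mantel-Hanzel relative risk with adjustment for stratification will be calculated comparing the two groups". Finally, "the proportions achieving blood pressure control at 3-months and 6-months follow-up will also be tabulated".

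The protocol has no numeric definition of the endpoint. It does use 140/90 mmHg for the eligibility readings (Table 3) and for the message loop (Aim 4, Intervention). There, participants with a raised reading are told "that the minimal goal is $<140/90$ mmHg for people with hypertension", and the congratulatory message is triggered below the same level. The Usual Care paragraph also uses a systolic level of 140 mmHg to identify the kiosk screen that it illustrates.

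**The concern.** The only sentence in either document that designates a primary endpoint carries a systolic limit that conflicts with the SAP's own analysis paragraph. Anyone who looks up the primary endpoint, whether to program it, report it or copy it elsewhere, finds 149.

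If that figure is used, participants with systolic pressure of 140 to 148 mmHg and diastolic below 90 count as successes. In the intervention arm, the same reading triggers a text saying that the participant is above goal.

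The definition feeds the control proportion in each arm, their difference, the stratified relative risk and the 3- and 6-month proportions. With no hypothesis test planned, these descriptive figures are the whole efficacy result. They inform the protocol's criterion of a favourable indication of effect before a larger trial, and they are natural inputs for planning that trial. Two written definitions also leave the cut-off open to choice, or to the appearance of choice, after the data are seen.

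**Working it through.** **Step 1. The thresholds side by side**

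| Place | Use | Systolic | Diastolic |
|---|---|---|---|
| SAP, opening paragraph | Primary endpoint, 12 months | <149 | <90 |
| SAP, Aim 4 | Control, 12 months; also tabulated at 3 and 6 months | <140 | <90 |
| Protocol, Table 3 | Eligibility readings | ≥140 | ≥90 |
| Protocol, Aim 4, Intervention | Stated goal and congratulatory message | <140 | <90 |
| Protocol, Aim 4, Usual Care | Kiosk screen illustrated | ≥140 | not given |

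The gap is 149 − 140 = 9 mmHg. Participants with systolic pressure of 140 to 148 and diastolic below 90 change class between the two SAP sentences. Nobody else does.

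**Step 2. Is there a planned figure to reproduce?** No. The documents give no assumed control rate, SD, alpha or power. The 70 per group (2 × 70 = 140 in total) was set as 10% of the planned full trial, so it does not depend on the cut-off.

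**Step 3. Effect on the control rate (assumed distribution)**

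Assume 12-month systolic pressure is normal with mean μ and standard deviation σ, and ignore the diastolic limit. The extra share classed as controlled is

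Φ((149 − μ)/σ) − Φ((140 − μ)/σ).

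At μ = 145 and σ = 16:
- <140: Φ(−5/16) = Φ(−0.3125) = 0.377
- <149: Φ(4/16) = Φ(0.25) = 0.599
- Difference: 0.222, or 22 points; 0.222 × 70 ≈ 16 participants per group.

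Over μ = 135, 140, 145, 150 and σ = 14, 16, 18, 20, the difference runs from 0.159 to 0.252. With whole-number readings (cut-offs at 139.5 and 148.5) and σ from 12 to 20, it runs from 0.161 to 0.291, about 11 to 20 of 70 per group.

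**Step 4. Effect on the comparison between groups**

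Assume also that the intervention lowers the mean by 5 mmHg, with usual-care mean 145, intervention mean 140, σ = 15 and whole-number readings.

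| Cut-off | Usual care | Intervention | Risk difference | Relative risk |
|---|---|---|---|---|
| <140 | Φ(−5.5/15) = 0.357 | Φ(−0.5/15) = 0.487 | 0.130 | 1.36 |
| <149 | Φ(3.5/15) = 0.592 | Φ(8.5/15) = 0.715 | 0.122 | 1.21 |

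With the same 5 mmHg shift, usual-care means of 140, 145 and 150, and σ of 12, 15, 18 and 20, the relative risk is lower under <149 in all 12 scenarios. It runs from 1.20 to 1.69 under <140 and from 1.13 to 1.37 under <149. The risk difference can move either way: from 0.163 to 0.109 at mean 140 and σ = 12, and from 0.133 to 0.164 at mean 150 and σ = 12.

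**The case against.** The best answer is that 149 is a slip in an introductory paragraph. Aim 4 is the operative text: it specifies the analyses and contains a complete definition. An analyst working from it would code 140 and never meet the problem. No alpha, power or sample size depends on the cut-off. The illustrated change is mainly in the control rate. In the central example the risk difference moves by about one point and the relative risk stays above 1, so the criterion of a favourable indication would still be met. The percentages rest on assumed distributions, and ignoring diastolic pressure makes them upper bounds for any given systolic distribution, because a participant with diastolic pressure of 90 or more is uncontrolled under both rules.

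Most of this stands, and it limits the weight. The results go wrong only if the opening sentence is the one followed. Aim 4 does not use the term primary endpoint, so linking the two sentences is an inference, though they describe the same outcome at the same time. The protocol's 140/90 figures concern eligibility and messaging, so they support the Aim 4 reading without defining the endpoint. But nothing in the SAP says that Aim 4 overrides the sentence that designates the primary endpoint, and that this is probably a typing error does not remove the conflict.

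**Conclusion.** The concern holds. The current SAP contains two incompatible definitions of 12-month control, and the one attached to the primary endpoint is out of line with everything else in both documents. This follows from the text alone and needs no assumption.

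The size does rest on assumptions: normal systolic pressure with mean 135 to 150 and SD 14 to 20 mmHg, diastolic limit ignored. Under these, coding 149 instead of 140 raises the control rate by 16 to 25 points. With a 5 mmHg benefit the relative risk is pulled towards 1, for example from 1.36 to 1.21, while the risk difference may hardly move. The sample size is unaffected. Because the conflict lies in the primary endpoint itself, it must be corrected.

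**What to change.** In the SAP's opening paragraph, define the primary endpoint as systolic pressure below 140 mmHg and diastolic pressure below 90 mmHg at 12 months after randomization, as in Aim 4. It would help to state in Aim 4 that the 12-month proportion is the primary endpoint, so that one definition serves throughout. Check any analysis code or other study record that took its definition from the opening paragraph.

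The cost is one corrected figure in the SAP. Sample size, data collection and the planned analyses do not change.

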## ROKHYT TRIAL PROTOCOL

**The specific aims of this protocol** are to:

1. Develop and pre-test the intervention text messages.
2. Pilot the enrollment, consent, randomization, and data collection procedures at baseline and 3, 6, and 12 months and document participation and completion rates in a randomized pilot study of N=70 per group.
3. Obtain demographic data on potentially eligible participants using an on-line questionnaire.
4. Pilot test the text messaging intervention and document blood pressure control rate in response to the intervention.
5. Pilot test secure data transfer and other data coordinating center (DCC) functions.

The following metrics will be used to decide whether to proceed with a larger trial: **Aim 1**. Successful piloting of text messages including tailored features, based on positive feedback from pilot subjects. **Aim 2**. Successful enrollment, consent, and randomization of N=70/group. **Aim 3**. Completion of >80% of all data fields. **Aim 4**. Completion of 12-month follow-up by >80% of those randomized; positive signal of intervention effect. **Aim 5**. Successful and secure transfer of all pilot data from higi to the DCC.

The overall goal is to provide pilot data to support an application to conduct a fully powered randomized controlled trial.

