#### **C. Trial: N = 140**

1. Invitation (Trial)
2. Consent (Trial)
3. HIPAA release for higi to give blood pressure data and email to Columbia
4. Baseline questionnaire (27 items)
5. Text messages – intervention
6. Text messages – reminders to return for 3, 6, and 12-month blood pressure measurements
7. Videos
9. Exit questionnaires (one for intervention group and one for usual care group)

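### Does the SAP need new output lines for the pilot's 12-month completion and data-field progression metrics?

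*SAP*

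**What the plan says.** The section headed ROKHYT TRIAL PROTOCOL introduces its list with "The following metrics will be used to decide whether to proceed with a larger trial". The Aim 3 metric is "Completion of >80% of all data fields". The Aim 4 metric is "Completion of 12-month follow-up by >80% of those randomized", together with a positive signal of effect. The other metrics are qualitative or simple counts.

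Under Aim 2 (Approach to Accomplishing the Specific Aims), the protocol:
- defines the completion rate as 12-month blood pressure completers over everyone randomized, and states that it will be computed;
- rules out replacing people who die, drop out or are lost;
- says Aim 3 data are collected on an electronic form filled in as part of consent, and describes blood pressure measurement separately.

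The SAP's Table 1 repeats that Aim 2 will "document participation and completion rates in a randomized pilot study of N=70 per group". Its analysis lines are shorter. Aim 2 reads "The numbers enrolled, consented, and randomized will be tabulated". Aim 3 reads "Demographic characteristics will be tabulated". For Aim 4, "The proportion in each group (intervention and control) achieving blood pressure control at 12 months will be tabulated", followed by the difference, a stratified relative risk, and the 3- and 6-month proportions. Aims 1 and 5 have no analysis.

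**The concern.** A pilot exists to inform a go/no-go decision, and Aim 5 of the protocol makes data summarization the main analysis. A SAP that lists no output for two of the numeric progression criteria therefore looks incomplete, all the more so because its own Table 1 promises completion rates.

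The data-field metric looks worse, since neither document states its denominator. Its wording could take in every form and visit. Aim 3 speaks of potentially eligible people, and item 1 of the Notes expects some to consent without finishing enrollment. If the fields and people were chosen after the data were seen, the same data might pass or fail, or pass with little follow-up.

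For completion, a single pooled figure could hide poor follow-up in one group. Only the intervention group receives return prompts beyond the shared study reminders, so a difference between groups is plausible. The SAP also does not say whether the Aim 4 proportions are taken over people randomized or people measured, so completion cannot be read from them with certainty.

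**Working it through.** **Inputs.** 70 per group, allocated 1:1 (Protocol, Phases of the project and Aim 2). Baseline questionnaire of 27 items (Protocol, C. Trial). Both thresholds are strictly above 80% (Protocol, opening section). Follow-up blood pressure at 3, 6 and 12 months, three readings each (Protocol, Aim 2).

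**Plan's own figure.** 2 × 70 = 140, which agrees with the trial N of 140.

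**Completion metric.** 0.80 × 140 = 112. 112/140 = 80.0% does not exceed 80%; 113/140 = 80.7% does (95% Wilson interval 73.4% to 86.4%). Threshold, numerator and denominator are all in the protocol, so nothing is left to choose. The most lopsided split of 113 is 70/70 against 113 − 70 = 43, and 43/70 = 61.4%. That is a bound, not a forecast.

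**Data-field metric, which fields.** Set side by side, the texts narrow this down. The metric carries the Aim 3 label; Aim 3 data collection is the electronic form completed at consent; blood pressure is described in a separate sentence; 12-month follow-up has its own metric under Aim 4. That leaves the 27-item form. Over those randomized, 27 × 140 = 3,780 responses and 0.80 × 3,780 = 3,024, so 3,025 are needed. Item 3 of the Notes places the form before randomization, so this version should be near complete. Whether items can be skipped is not stated.

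**Data-field metric, which people.** Suppose all 140 randomized people complete the form and k further consenters leave it wholly blank. The rate is 140/(140 + k).
- k = 34: 140/174 = 80.5%, pass.
- k = 35: 140/175 = 80.0%, fail.

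The documents give no value for k. Under item 3 of the Notes the HIPAA release comes after the questionnaire, so a person who drops out there has already filled in the form. If, as an assumption, half of the k had done so, the rate is (140 + 0.5k)/(140 + k). This exceeds 0.80 when 28 > 0.3k, that is, up to k = 93 (186.5/233 = 80.04%); k = 94 fails (187/234 = 79.9%).

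**Wider reading, with blood pressure fields added.** Let f be the completed fraction of follow-up fields, with baseline items complete.
- 3 occasions × 3 readings × 2 values = 18 fields: (27 + 18f)/45 > 0.80 needs f > 0.50.
- Adding one baseline reading (2 fields): (29 + 18f)/47 > 0.80 needs f > 0.478.
- Adding three baseline readings (6 fields): (33 + 18f)/51 > 0.80 needs f > 0.433.
- One reading per follow-up occasion, no baseline reading: 27/33 = 81.8% at f = 0.

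The threshold moves with whichever fields one lists, so none of these values describes the plan. In every version, the Aim 4 metric still requires 113 of 140 at 12 months.

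**The case for a change.** The best argument for a change is that a SAP should list what will be reported, and here it omits criteria that the protocol says will guide the decision. The cost would be a few lines of wording. The data-field metric does leave room for choice: the Aim 3 label points to the baseline form, but the word *all* can be read more widely, and consented against randomized is unsettled. The weekly coordinating-center reports are for monitoring and do not define a denominator.

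Part of this stands. The SAP does omit both rates, and the people counted for the field metric are not stated. The participation rate defined under protocol Aim 2 has no SAP line either, but no progression metric uses it.

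The rest does not carry a change. For completion, the request is that the SAP restate a protocol commitment. The route to passing with little follow-up is closed by the separate 12-month criterion. Thirty-five wholly blank forms and a 70-to-43 split are assumed or extreme inputs. By-group completion rates and confidence intervals would be reasonable additions, but the protocol's metric is pooled and the pilot is deliberately descriptive. Whether the Aim 4 proportions use people randomized or measured is a missing-data question about the endpoint, not about these metrics.

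**Conclusion.** No change to the plan follows. The SAP is thinner than the protocol here, but no stated rule gives a wrong figure. Analysts working from both documents would compute 12-month completion over the 140 randomized, passing at 113 or more. They would compute data-field completeness from the 27-item baseline form, passing at 3,025 of 3,780 if counted over those randomized.

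The remaining ambiguity is the set of people counted for the field metric. It alters the result only if many consenters leave the form unfinished: at least 35 if their forms are wholly blank, more if some had completed it. The documents give no number for this.

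The conclusion rests on two readings: that the Aim 3 label ties the field metric to the consent-stage form, and that the protocol's definition of completion governs where the SAP is silent. If *all data fields* was meant to span every visit, the field metric would be less informative, but the separate retention criterion would still protect the decision. No estimate, endpoint or sample size is affected.

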- \$100 at 12-month blood pressure check and final survey. All higi communications are available in English or Spanish as selected by the individual. **Eligibility** criteria are shown in table 3. **Consent** will be obtained electronically, also in English or Spanish. **Randomization** will be stratified by sex, age (18-55, 56-85 years), and region of the country (northeast, southeast, north central/west, south central/west), assigned 1:1, and performed by the DCC using the web-based trial management system. Participants will receive email informing them that they have been enrolled and which group has been assigned. **Data collection** for Aim 3 will be accomplished using an electronic form with multiple-choice or numeric response sets on the secure web portal, to be completed as part of the consent process. We will obtain BP measurements at the kiosk at time of enrollment and at 3, 6, and 12 months post randomization. For follow-up measurements, subjects will receive email messages prompting them that it is time to obtain a study BP measurement at a kiosk along with instructions about how to take the BP, specifically to take all of their usual medications the day they take the BP, to log in at the kiosk using their account identifier (email address) when they take the BP, and to take the BP three times at intervals of about one minute. Subjects will receive up to \$200 in Bank of America pay card by mail when completing each blood pressure check points. **Participation rate** will be calculated as the proportion of those invited to participate and eligible who consent and complete the baseline questionnaire and BP measurement. **Completion rate** will be calculated as the proportion of those randomized who complete the 12-month follow-up BP measurement. We do not propose to replace randomized individuals who die, drop out, or are lost to follow-up in either the pilot or the full scale study.

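### Does leaving the 12-month denominator unstated, and not listing the completion rate among the SAP outputs, undermine the pilot's go-ahead decision?

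*SAP*

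**What the plan says.** SAP Table 1 gives Aim 2 the task to "document participation and completion rates in a randomized pilot study of N=70 per group". The SAP's analysis line for Aim 2 is shorter: "The numbers enrolled, consented, and randomized will be tabulated". For Aim 4 it states: "The proportion in each group (intervention and control) achieving blood pressure control at 12 months will be tabulated". It adds the difference in proportions and a Mantel-Haenszel relative risk adjusted for stratification, and rules out formal testing.

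The protocol's text on Aim 2 defines participation as "the proportion of those invited to participate and eligible who consent and complete the baseline questionnaire and BP measurement". The completion rate "will be calculated as the proportion of those randomized who complete the 12-month follow-up BP measurement". On losses it says: "We do not propose to replace randomized individuals who die, drop out, or are lost to follow-up". The opening list of metrics for proceeding to a larger trial includes, under Aim 4, "Completion of 12-month follow-up by >80% of those randomized", together with a favourable signal of effect.

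Under Aim 4, Intervention, a participant in the intervention group with a raised reading gets a message "asking them to return to a higi kiosk in 2 weeks to have the blood pressure taken". After a controlled reading the recall is at one month, and a missed return brings weekly texts. Usual care has no such loop. Notes item 4 of the protocol sends reminders for the endpoint measurements to both groups, and Aims 2 and 4 pay both groups for follow-up checks.

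**The concern.** Numbers enrolled, consented and randomized cannot yield a 12-month completion rate, which needs the count measured at 12 months. They cannot yield the participation rate either, which needs the number invited and eligible. Read alone, the SAP has no output for one part of the protocol's Aim 4 metric.

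The other part, the signal of effect, would be read from the Aim 4 difference, whose denominator is open. If the return loop makes intervention participants likelier to turn up at 12 months, counting absentees as uncontrolled favours the intervention, while restricting to those measured does not do so mechanically. A choice made after seeing the data could turn a slightly negative result into a slightly positive one, and these figures are meant to support the application for the full trial.

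**Working it through.** **Inputs.** From the documents: 70 per group, 140 in total (2 × 70 = 140, matching the protocol's trial phase); completion above 80%; no replacement of losses; no test. Assumed, because the documents give no figures: completers per group, and control rates of 30% to 50% (up to 55% in the intervention group when an effect is assumed).

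**1. Missing outcomes the criterion allows.** 112/140 = 80.0% does not exceed 80%; 113/140 = 80.7% does. Up to 140 − 113 = 27 outcomes may be missing. If each were resolved in the direction that most favours one group, then the other, the difference would move by 27/70 = 38.6 points. That is an extreme bound, not a likely error.

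**2. How the two readings relate.** With x controlled and n measured in each group (I intervention, C control), the crude relative risk among all randomized, missing counted as not controlled, is

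(x_I/70)/(x_C/70) = [(x_I/n_I)/(x_C/n_C)] × (n_I/n_C).

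With equal completion the sign cannot change. The identity holds for the crude ratio only. The SAP plans a stratified ratio, whose weights also shift with the denominators, so completion by group alone would not convert one planned estimate into the other.

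**3. A reversal is possible.** Take 60 and 53 completers (113/140) with 24 and 22 controlled.
- Measured only: 24/60 − 22/53 = 40.0% − 41.5% = −1.5 points; ratio 0.96.
- All randomized: 24/70 − 22/70 = 34.3% − 31.4% = +2.9 points; ratio 1.09.
- Check: 0.964 × 60/53 = 0.964 × 1.132 = 1.091.

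**4. How often.** With independent binomials X ~ Bin(n_I, p_I) and Y ~ Bin(n_C, p_C), the chance of opposite signs is P[(X − Y)(X/n_I − Y/n_C) < 0].

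| Completers (I vs C) | True control (I vs C) | Opposite signs |
|---|---|---|
| 57 vs 56 | 40% vs 40% | 0% |
| 58 vs 55 | 40% vs 40% | 7% |
| 60 vs 53 | 40% vs 40% | 17% (12.5% at 30%, 21% at 50%) |
| 63 vs 50 | 40% vs 40% | 31% |
| 60 vs 53 | 50% vs 40% | 9% |
| 60 vs 53 | 55% vs 40% | 4% |
| 53 vs 60 | 50% vs 40% | 14% |

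**5. How large.** At 60 vs 53 with no effect, when the signs disagree, the measured-only difference averages 2.0 points in size and the all-randomized difference 2.4. The 95% sampling interval at 40% control with 70 per group is 2 × 1.96 × √(2 × 0.4 × 0.6/70) = 0.325, about 32 points wide.

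**6. What the documents already supply.** The completion metric is set on everyone randomized, so it can be judged without a table by group. Its numerator and denominator are defined in the protocol. Aim 5 of the protocol has the data coordinating center report follow-up measurements weekly. Both versions of the Aim 4 result come from six counts: randomized, measured and controlled, in each group. Tabulating the proportions requires them.

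**The case for a change.** The strongest case for a change is that without a test these descriptive figures are the evidence, and that the loop promotes attendance at the place where the endpoint is measured. With no effect and 60 vs 53 completers, the all-randomized difference is positive 67% of the time, against 50% among those measured; at 63 vs 50 it is 82% against 51%. Return behaviour alone could then look like benefit, and a sentence in the SAP would settle it. A related worry is that a loop reading near 12 months might be counted as the endpoint in one group only.

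Part of this stands. The denominator is unwritten, and the SAP's Aim 2 line is shorter than its own aim. The rest is weaker. Unequal completion is assumed, and shared endpoint reminders and payments work against it. Nothing in the protocol equates a favourable signal with the bare sign of the difference. Neither denominator is wrong for a descriptive pilot. Counting absentees as uncontrolled imports attendance into the result; restricting to those measured risks selection. Requiring both to agree is not neutral either: with no effect and 53 vs 60 completers it cuts the chance of a positive result to 26%. On loop readings, the protocol's Aim 2 describes a prompted study measurement with three readings about a minute apart, and a diagram that may say more is not reproduced.

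**Conclusion.** The omission is real but is missing detail, not a rule that produces a wrong answer. The protocol supplies the rate definitions that the SAP does not repeat, and the open denominator is a presentation choice between two usable summaries that come from the same counts. A sign reversal needs unequal completion and a small difference. In the illustrative case it occurs 17% of the time under no effect and 4% to 9% under an assumed 10- to 15-point benefit, and it concerns differences of about 2 points that a pilot of 70 per group cannot distinguish from zero in any case. These figures rest on assumed completer counts and control rates and on return being unrelated to blood pressure. A much larger completion gap would make the choice matter more, but it would be visible in the counts needed to form the proportions. Stating the denominator would be tidy; the plan does not depend on it.
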